### **6.4.2.1 Number of inhalations of Rescue Medication**

The total number of inhalation used of rescue medication (number of puffs taken in the previous 12 hours) will be recorded morning and evening by the patient, in the eDiary.

The patient will input the number of puffs of rescue medication they have used during the 12 hours previous. The patients mean evening and morning rescue medication usage will be automatically be calculated by the eDiary. This SABA data collected by the patient during the last 7 days of screening will be used to set alerts to the patient to contact the investigator in case of worsening asthma (see [Section 6.4.4](#) Asthma worsening criteria).

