The post-baseline measurements start with the morning recordings at Day 2 and end with the evening recordings at the day of last dose. Similar calculations as for baseline data will be done. For the first 26 weeks and the whole 52 weeks, summary values will only be calculated if a patient has at least 30% of their diary days and at least 20 diary days with evaluable data for that variable in the period of interest. For 4-week intervals (defined as 28 days), summary values will only be calculated if a patient has at least 50% of their diary days (i.e. 14 days) of non-missing data. If there will be less than 14 days with data in a 4-week period, then the data should collapse with the previous 4-week interval. The mean morning/evening PEF and the mean change from baseline will be summarized for the first 26 weeks (defined as up to Visit 107), and for the whole 52 weeks of treatment period (defined as up to Visit 111), and will be summarized by 4 weekly interval.

Rescue medication

The total number of puffs of rescue medication per day over the first 26 weeks and over the 52 weeks will be calculated and divided by the total number of days to derive the mean daily number of puffs of rescue medication taken for the patient.

The baseline and post-baseline values are defined in the same way as for the PEF.

The mean daily number of puffs of rescue medication use will be calculated for each patient over the first 26 weeks of treatment period, over the whole 52 weeks of treatment period and over the screening period (which will be used as the baseline value) as described for the PEF. This will be done separately for morning (night-time), evening (daytime), and daily (night-time plus daytime) rescue medication use. If for the value over the whole day (24 hours) the number of puffs is missing for part of the day (either day-time or night-time) then a half day will be used in the denominator to calculate the average value. Any values > 30 for the number of puffs of rescue medication in a 12 hour period will be set to missing. These high numbers are not realistic and could impact the analyses. Where the number of puffs of rescue medication is missing but the rest of the e-diary has non-missing data, the number of puffs will be assumed to be zero.

The mean daily number of puffs of rescue medication use over the first 26 weeks and over the 52 weeks of treatment and the mean change from baseline will be summarized.

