In addition, the mean number of puffs of rescue medication in the morning and in the evening, and the percentage of 'rescue medication free days' (defined as any day where the patient did not use any puffs of rescue medication during daytime and night-time) will be summarized.

Asthma Control Questionnaire 7 (ACQ-7)

The baseline value is defined as the score obtained at Day 1. If the value is missing, the last measurements from screening visit 2 or unscheduled screening visits will be used.

ACQ-7 and the change from baseline at 12, 26 and 52 weeks of the study treatment will be summarized.

The proportion of patients who achieve an improvement of at least 0.5 in ACQ-7 (i.e., a decrease of ACQ-7 score of at least 0.5 from baseline) at 26 and 52 weeks visits will be summarized.

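### Mean daily rescue use pools morning and evening diary sessions, so it leans toward the better-recorded half of the day when the two halves differ (low severity)

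*SAP*

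**What the plan says.** Protocol section 6.4.2.1 sets two diary entries a day, each with a 12-hour recall: "The total number of inhalation used of rescue medication (number of puffs taken in the previous 12 hours) will be recorded morning and evening".

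SAP section 2.6.2 (Rescue medication) builds the endpoint from these entries.

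- **Base formula.** Puffs are totalled over the period and "divided by the total number of days to derive the mean daily number of puffs of rescue medication taken for the patient".
- **Three variables.** "This will be done separately for morning (night-time), evening (daytime), and daily (night-time plus daytime) rescue medication use".
- **Half-day rule.** If one part of the day is missing, "either day-time or night-time) then a half day will be used in the denominator to calculate the average value".
- **Implausible values.** "Any values > 30 for the number of puffs of rescue medication in a 12 hour period will be set to missing". This is a second way for a half-day to arise.
- **Zero-fill.** "Where the number of puffs of rescue medication is missing but the rest of the e-diary has non-missing data, the number of puffs will be" set to zero. The SAP does not say whether the rest of the diary means that session's entry or that day's entries.
- **Minimum data.** Baseline and post-baseline values follow the PEF rules. A 26- or 52-week value needs "at least 30% of their diary days and at least 20 diary days with evaluable data for that variable in the period of interest", and a baseline needs at least 7 days with data. No minimum is set per session for the daily variable.
- **Rescue-free days.** These are "defined as any day where the patient did not use any puffs of rescue medication during daytime and night-time".

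Change from baseline in rescue use is a secondary endpoint (Protocol Table 2-1, SAP section 1.2). Protocol section 9.5.1 gives only total puffs over total days and has no half-day rule.

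**The concern.** Giving every recorded session a weight of half a day treats night and day sessions as interchangeable. They are not if a patient uses more rescue medication in one half of the day than in the other. When the evening entry is missed more often than the morning entry, the daily mean moves toward twice the night-time use. When mornings are missed more often, it moves the other way.

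What is at stake is the accuracy of one descriptive secondary endpoint. Its baseline comes from a short screening diary, and its treatment values come from up to 52 weeks of twice-daily entries. The balance of morning and evening completion, and the day-night gap in use, could each differ between the two periods.

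**Working it through.** **Inputs.** The half-day weight and the base formula come from SAP section 2.6.2. The documents give no rescue-use level, no day-night split and no diary completeness, so there is no plan figure to reproduce, and the values of n, d, a and b below are assumptions. I take the denominator to be recorded days, with whether a session is recorded unrelated to its puff count within each half of the day. I also take zero-fill to work per session, so a wholly missed session stays missing.

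**Formula.** Per calendar day, expected recorded puffs are a·n + b·d, and the expected denominator is 0.5a + 0.5b. So

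SAP value = 2(a·n + b·d)/(a + b).

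The target is n + d. Subtracting gives

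bias = (a − b)(n − d)/(a + b).

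The bias is zero if a = b or if n = d.

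**Level, true value 4.0 puffs/day.**

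| n, d | a, b | SAP value | Bias |
|---|---|---|---|
| 1, 3 | 0.90, 0.90 | 4.00 | 0 |
| 1, 3 | 0.95, 0.90 | 2(0.95 + 2.70)/1.85 = 3.946 | −0.054 (−1.4%) |
| 1, 3 | 1.00, 0.90 | 2(1 + 2.70)/1.90 = 3.895 | −0.105 (−2.6%) |
| 1, 3 | 1.00, 0.70 | 2(1 + 2.10)/1.70 = 3.647 | −0.353 (−8.8%) |
| 1, 3 | 0.70, 1.00 | 2(0.70 + 3)/1.70 = 4.353 | +0.353 (+8.8%) |
| 2, 2 | 1.00, 0.70 | 2(2 + 1.40)/1.70 = 4.00 | 0 |

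The sum of the two session means is 4.0 in every row.

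**Simulation check.** With 4000 patients, 364 days, Poisson puffs, n = 1, d = 2, a = 0.90 and b = 0.70, the SAP rule gave 2.87 against a true 3.00 (formula: 2.875). Summing the two means gave 3.00.

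**Change from baseline, true change −2.0.**

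- Use falls from 1/3 to 0.5/1.5, with a complete baseline. On-treatment completeness of 1.00/0.70 gives 2(0.5 + 1.05)/1.70 = 1.824, a change of −2.18. At 0.95/0.90 the on-treatment bias is 0.05 × (−1)/1.85 = −0.027, a change of about −2.03.
- Completeness is 0.90/0.70 in both periods and use falls from 1.5/2.5 to 0.5/1.5, so the gap stays at 1.0. The bias is −0.125 in each period and cancels, giving −2.00.
- Completeness is the same, but use falls to 0.75/1.25, so the gap narrows to 0.5. The on-treatment bias is 0.20 × (−0.5)/1.60 = −0.0625, and the change is −1.94.

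**Zero-fill read per day instead.** A missed session then becomes 0 puffs with a full day in the denominator. With n = 1, d = 3 and 1.00/0.70, the value is 1 + 0.70 × 3 = 3.1 (−22.5%), and the half-day rule would rarely apply. Zeros would also enter the daytime mean, so summing the two means would not help. The reading of this sentence therefore matters more than the half-day weight.

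**The case against.** The half-day rule is a sensible convention. Counting half-recorded days as whole days would give 3.1 in the 100%/70% case, against 3.65 under the SAP rule and a true 4.0, so the rule already removes much of the error. It applies to baseline and treatment alike. Both sessions use the same device and pair the puff count with PEF (Protocol Appendix 4), and the diary is reviewed at clinic visits, so nothing in the documents points to unequal completion. Separate morning and evening means are planned, which lets a reader see the components. All of this stands, and it keeps the severity low. It does not make the pooled weighting correct.

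A reader might infer three stronger points that the documents do not support.

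- **Lower diary completion on treatment biases the change by itself.** It does not. If completion falls from 95% to 60% equally in both sessions, then a = b and the bias is zero.
- **Half-recorded days count as rescue-free.** The definition refers to no puffs in daytime and night-time, which on its face needs both halves. Only the place of half-recorded days in the denominator is unstated.
- **The error is large.** Losing half of the evening entries with no mornings lost would give 2(1 + 1.5)/1.5 = 3.33 (−16.7%), but that is a chosen scenario.

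**Conclusion.** The point holds as a low-severity definition issue. As written, the daily mean is biased by (a − b)(n − d)/(a + b) when one session is recorded more completely than the other and use differs between night and day. With 1 puff at night and 3 by day, the bias runs from about −1.4% (95%/90%) to −8.8% (100%/70%), and it has the opposite sign if mornings are the session more often lost. In the change from baseline it cancels only partly, or not at all, unless both the completeness imbalance and the day-night gap hold steady.

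These sizes rest on assumed inputs and on the per-session reading of zero-fill. The primary safety analysis, the sample size and the separate morning and evening means do not depend on the half-day rule.

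**What to change.** In SAP section 2.6.2:

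1. Define mean daily puffs as mean night-time puffs plus mean daytime puffs, each averaged over its own recorded sessions, at baseline and on treatment. This replaces the half-day denominator and fits the SAP's own description of the daily variable as the two parts together.
2. Apply the existing minimum-data rule to each component separately.
3. State that zero-fill works per session: the puff count is missing but the rest of that session's entry is present. A wholly missed session then stays missing.
4. As a clarification only, state that days with just one session recorded are left out of the denominator for rescue-free days.

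The cost is wording, since the SAP already plans both component means. The downside is that a few patients with too few entries in one half of the day lose the daily value. The change corrects the weighting only. If missed sessions tend to be high-use or low-use sessions within their own half of the day, neither definition repairs that.

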2.6.2 Statistical hypothesis, model, and method of analysis

Spirometry

For FEV₁ and FVC, the baseline is defined as the mean of the values taken in the clinic at 45 and 15 min prior to first dose at Visit 101. If one of the -45 and -15 min values is missing (or is not confirmed to be pre-dose) then the remaining non-missing value will be taken as the

baseline. If both values are missing (or not confirmed to be pre-dose), then the last out of the pre-bronchodilator measurements taken at the screening Visits 2 or at unscheduled screening visits will be used as the baseline. If the FEV₁, FVC measurements are missing both on Day 1 and at screening visits, the respective baseline values will be set to missing.

The pre-dose FEV₁ is defined as the mean of the pre-dose 45 and 15 min FEV₁ values. The pre-dose FVC is defined as for the pre-dose FEV₁. If any of the pre-dose 45 and 15 min values contributing to the pre-dose value are collected within 7 days of systemic corticosteroid use, 6 hours of rescue medication use, or actual measurement times are post-dose will be set to missing. If one of the two values is missing (or set to missing) then the remaining non-missing value will be taken as pre-dose value. If both values are missing, then pre-dose value will be missing.

The pre-dose FEV₁ and the change from baseline at 12, 26 and 52 weeks of the study treatment will be summarized with descriptive statistics. Summaries will be repeated for pre-dose FVC.

In addition, the means in pre-dose FEV₁ and pre-dose FVC for each visit will be displayed graphically.

Peak Expiratory Flow Rate (PEF)

PEF(liters/min) will be analysed separately for morning and evening values.

The baseline values are defined as the average from all non-missing records taken in the screening period for 14 days before Day 1 administration (in case they were measured before the first intake of study drug as scheduled in the study protocol). When calculating the baseline value there is no limitation to the 14 days immediately prior to Day 1 administration. If a patient has less than 7 days with non-missing data, then the respective baseline value will be set to missing.

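### As printed, the SAP scores a 12-hour rescue count of 31 as zero puffs: counts above 30 become missing, and missing counts then become zero

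*SAP*

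**What the plan says.** The Rescue medication part of SAP 2.6.2 gives three rules that can all bear on the same 12-hour count:

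- **Half-day rule.** If the count is missing for the daytime or the night-time, "then a half day will be used in the denominator to calculate the average value".
- **Cut-off rule.** "Any values > 30 for the number of puffs of rescue medication in a 12 hour period will be set to missing". The reason given is: "These high numbers are not realistic and could impact the analyses".
- **Zero rule.** Where the puff count "is missing but the rest of the e-diary has non-missing data, the number of puffs will be assumed to be zero".

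No order of execution is stated. Nothing says whether a count removed by the cut-off rule counts as missing for the zero rule.

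Three other parts of SAP 2.6.2 matter. For rescue use, "The baseline and post-baseline values are defined in the same way as for the PEF", and the PEF text says "The baseline values are defined as the average from all non-missing records taken in the screening period". The percentage of rescue-free days is summarised, each "defined as any day where the patient did not use any puffs of rescue medication during daytime and night-time"; Protocol 9.5.1 adds that this is judged from diary data. The spirometry text, by contrast, says "If one of the two values is missing (or set to missing", so there it names removed values explicitly.

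Protocol 9.5.1 and SAP 2.6.3 say that missing efficacy data are not imputed, SAP 5.1 says no imputation is planned, and SAP section 4 declares no departure from the protocol analyses. The protocol's own rescue text contains neither the cut-off rule nor the zero rule.

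**The concern.** The reason given for the cut-off supports discarding an implausible count. It does not support treating that count as evidence of no use. Read in sequence, however, the rules do the latter: the cut-off creates a missing count, and a session holding an entry of 31 will normally also hold PEF and symptom answers, so the zero rule's condition is met. The highest entries in the diary would be turned into the lowest possible value.

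Change from baseline in rescue use is a named secondary endpoint (Protocol Table 2-1, SAP 1.2), and rescue-free days are summarised with it. The rules apply at baseline and after it. A high baseline entry scored 0 understates the reduction in rescue use; a high on-treatment entry scored 0 overstates it. The direction therefore depends on where such entries fall.

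Two related gaps concern ordinary blanks. The half-day and zero rules can both claim the same missing half-day, and no precedence is given. The phrase about the rest of the e-diary is also undefined, although Protocol Appendix 4 sets out separate morning and evening sessions. Finally, the zero rule sits beside general statements that nothing is imputed.

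**Working it through.** **Inputs from the documents.** Cut-off above 30 puffs per 12 hours, half-day denominator, zero rule, 14-day baseline with a 7-day minimum (SAP 2.6.2); 66 treated patients (Protocol 9.8, SAP 3). No figure of the plan is in dispute. The 66 reproduces: 100 − 41 = 59 and 59/0.90 = 65.6, rounded up to 66.

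**Assumptions.** The documents give no frequency for counts above 30, so every example below is illustrative. The reference patient uses 2 puffs per half-day, or 4 per day, over 182 days (26 weeks) or 364 days (52 weeks).

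**Step 1: the rules in printed order.**

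| Recorded count | Rest of diary entry | Score as printed | Score if removed counts stay missing |
|---|---|---|---|
| 30 | present | 30 | 30 |
| 31 | present | 0 | missing |
| 31 | absent | missing | missing |
| blank | present | 0 | 0 |

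**Step 2: one entry above 30 in one patient.** With h half-days and the removed count left missing, the mean is 2(h − 1)/((h − 1)/2) = 4.00 for any h. Scored as zero:

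- 26 weeks: 2 × 363/182 = 3.99
- 52 weeks: 2 × 727/364 = 3.99
- 14-day baseline: 2 × 27/14 = 3.86
- 7-day baseline: 2 × 13/7 = 3.71

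One affected 14-day baseline among 66 patients moves the group mean by (4 − 3.857)/66 = 0.002 puffs/day.

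**Step 3: repeated entries.** In a 28-day interval (56 half-days) with k entries of 31, the mean is 2(56 − k)/28 as printed: 3.93, 3.79 and 3.50 for k = 1, 3 and 7. It stays at 4.00 if the removed counts stay missing.

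**Step 4: rescue-free days.** A day of 0 + 31 becomes 0 + 0. If the definition is applied to the derived counts, that day is rescue-free and adds 1/182 = 0.55 percentage points over 26 weeks, or 1/364 = 0.27 over 52 weeks, for that patient.

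**Step 5: which rule comes first.** A day of 2 + 31 contributes 2 puffs over 1 day under the zero rule (a rate of 2.0) and 2 puffs over 0.5 day under the half-day rule (a rate of 4.0). The SAP reports period means and not single days, so this shows only that the two rules differ.

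**Step 6: ordinary blanks.** Assume 5% of half-days are blank and true use is 2.00 puffs/day. If blanks hide average use, the zero rule gives 2 × 0.95 = 1.90. If blanks mean no use, the half-day rule gives 2/0.95 = 2.11. Either rule can err, and the documents do not show what a blank means, so no direction is claimed.

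**The case against.** The strongest reply is that this is an ambiguity and not an error. The SAP states no order of execution, and sentence order need not be the algorithm. The zero rule can be read as covering only an item the patient skipped while answering the others, and a programmer might well apply it that way or run it before the cut-off. The spirometry wording cuts both ways: if the SAP separates missing from set to missing, then the bare word in the zero rule could mean blank only. The rescue-free definition speaks of puffs used, so a diary showing 31 arguably fails it whatever the derived count. The numerical effect is negligible, the trial is single-arm and descriptive, and the explicit zero rule in 2.6.2 can be read as a specific exception to the general no-imputation statements.

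Much of this stands as a description of likely intent and size. The PEF rule of averaging non-missing records supports the view that removed values should drop out. The rescue-free consequence does depend on applying the definition to derived counts. What does not stand is that the text settles the matter. No sentence in either document exempts removed counts, and a literal implementation scores 31 as 0. The spirometry usage is not consistent enough to decide it: its closing sentence, on both values being missing, appears to cover values set to missing too. The imputation conflict needs no assumption about order, and an exception should be declared where the SAP says there are none.

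**Conclusion.** The point holds. Applied literally, and provided the rest of the diary entry is present, SAP 2.6.2 turns an implausibly high rescue count into no use, a score that nothing in the diary supports. The zero rule also contradicts the no-imputation statements in Protocol 9.5.1 and SAP 2.6.3 and 5.1, and is not declared in SAP section 4.

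The size is small: about 0.01 puffs/day for a 4 puffs/day patient over 26 or 52 weeks, 0.14 in a 14-day baseline, and 0.002 on the group baseline mean for one affected patient. These figures assume a single entry above 30; the true frequency is unknown and may be nil. Only descriptive secondary summaries are affected, not the primary adverse event endpoint or the sample size. It should be corrected because the correction is nearly free, not because results would move much.

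**What to change.** In SAP 2.6.2 (Rescue medication), state that:

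1. Counts above 30 stay missing, are handled by the half-day denominator, are never set to zero, and cannot make a day rescue-free.
2. The zero rule applies only to a count left blank within an otherwise completed morning or evening session, and there takes precedence over the half-day rule. A missed session is handled by the half-day denominator.

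Then declare the zero rule as an exception in SAP 2.6.3, section 4 and 5.1. It need not be dropped for ordinary blanks, because the documents do not show whether a blank means no use.

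The cost is one exempting clause, one sentence on scope and order, the declared exception and one derivation step. The only downside is slightly fewer evaluable half-days.

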2.6.3 Handling of missing values/censoring/discontinuations

No imputation will be done for missing data.

2.7 Safety analyses

All safety variables will be summarized with descriptive statistics for the Safety Set.

Baseline is defined as the last measurement before first dose of the study drug, unless otherwise specified.

No imputation will be done for post-baseline missing data.

Post-baseline measurements comprise recordings up to the last dose of study drug + 7 days for laboratory, ECG, vital signs, non-serious AE and up to the last dose of study drug + 30 days for SAEs and death.

2.7.1 Adverse events (AEs)

Refer to the AEs analyses described in [Section 2.5](#) in this document.

2.7.1.1 Adverse events of special interest / grouping of AEs

Refer to the AEs analyses described in [Section 2.5](#) in this document.

Deaths

A summary of deaths according to the affected primary system organ class and preferred term for the investigator-reported principal cause of death and for the adjudicated cause of death will be separately presented regardless of study drug relationship.

All the deaths in the clinical database will be listed with both the investigator-reported principal cause and the adjudicated cause presented side by side, but only those between the first treatment and (the last dose + 30 days) will be included in summary tables.

See [Section 2.5](#) in this document as well.

